2.4 Hypotheses

H₀ - There will be no significant improvements in speech-intelligibility in noise, cognition and self-reported hearing abilities for experienced adult hearing aid users in either the experimental or control group.

H₁ - Auditory training will result in significant improvements in speech intelligibility in noise, cognition and self-reported hearing abilities of experienced adult hearing aid users (experimental group). These improvements will be significantly greater than for participants who do not receive the auditory training programme (control group).

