2.1 Research Aims and Objectives

This study will form a randomised controlled trial (RCT) investigating the effect of a novel auditory training intervention. The primary aim is to explore whether the training programme can improve speech intelligibility in noise for experienced adult hearing aid users. A secondary aim is to investigate the effect of training on self-reported listening and cognitively demanding tasks, as cognition has been shown to mediate speech perception.

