2.6.2 Measured Outcomes and Data Analysis

An ANCOVA will be used to assess any main effects of time or group on participants' performance on the QuickSIN, HHIE, Glasgow disability, MCRM or dual-task performance using initial performance on the QuickSIN as a covariate.

Table 2 Data to be collected during study

Data	Source
Age	At initial appointment from Auditbase
Gender	At initial appointment from Auditbase
Four-frequency average hearing levels	At initial appointment from Auditbase
Number of hearing aids (plus aided ear if	At initial appointment from Auditbase
unilateral fitting)	
Average hours of hearing aid use per day	At initial appointment from Auditbase
Initial HHIE	At initial appointment
Initial Glasgow disability	At initial appointment
Initial QuickSIN SNR loss	At initial appointment
Initial MCRM score	At initial appointment
Initial single task sore	At initial appointment
Initial dual task score	At initial appointment
Final HHIE	At final appointment
Final Glasgow disability	At final appointment
Final QuickSIN SNR loss	At final appointment
Final MCRM score	At final appointment
Final single task score	At final appointment
Final dual task score	At final appointment
Compliance	At final appointment from training diary

3 Project Considerations

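### The null hypothesis is about improvement within either arm on any of three domains, not a between-arm difference on QuickSIN, so shared retest gains reject it and it is not the complement of H1

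*Protocol*

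**What the plan says.** Section 2.4 sets the null as no significant improvement in speech in noise, "cognition and self-reported hearing abilities for experienced adult hearing aid users in either the experimental or control group". The alternative has two parts. Training improves all three domains in the experimental arm, and "These improvements will be significantly greater than for participants who do not receive the auditory training programme (control group".

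Section 2.6.2 plans an ANCOVA for "any main effects of time or group" on "QuickSIN, HHIE, Glasgow disability, MCRM or dual-task performance", with initial QuickSIN as covariate. It gives none of the five outcomes a special status.

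Elsewhere the Protocol does rank them. Section 2.1 states: "The primary aim is to explore whether the training programme can improve speech intelligibility in noise for experienced adult hearing aid users". It puts self-report and cognition under a secondary aim. Section 2.3 labels the speech perception question primary and the cognitive question secondary. Section 2.5.2 sizes the trial on a QuickSIN effect of 0.8, with 25 per group for 80% power at 5% significance.

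**The concern.** A randomised trial with a placebo-trained control arm exists to compare the arms, yet that comparison has no matching null. H0 concerns change over time within each arm, so it is contradicted by anything that makes scores rise between two visits four weeks apart, including familiarity with the tests. Controls sit the same tests at both visits and do the same period of conversation practice in quiet (section 2.5.6). The Protocol itself allows for practice effects: section 2.5.8 has the single and dual tasks given twice at the first visit for that reason.

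At stake is what the trial may conclude. Under the stated pair, several plausible results reject the null and yet fall outside the alternative. The outcome on which the trial was sized has no deciding role in either the hypotheses or the analysis section.

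**Working it through.** **1. The Protocol's own figure.** Normal approximation, two-sided 5%, 80% power, d = 0.8: n = 2(1.960 + 0.842)²/0.8² = 24.5, so 25 per group. This reproduces section 2.5.2. (The exact t-test gives 25.5, so 26, with 79.1% power at 25. A one-sided test would need 20, so a two-sided 5% is taken as intended.) The figure describes one between-arm comparison on one outcome.

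**2. Possible results against the stated hypotheses.** H0 is read in its plain sense: no significant improvement in any domain in any arm.

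| Result | H0 as worded | H1 as worded |
|---|---|---|
| Equal gains in both arms | rejected | not met (no superiority) |
| Gain in controls only | rejected | not met |
| Training better than control on QuickSIN only | rejected | not met (three domains claimed) |
| Training better in all three domains | rejected | met |

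Three of the four results reject the null without supporting the alternative.

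**3. Chance rejection with no true change.** H0 speaks of improvements, so each two-sided 5% test counts in one direction only, at 2.5%. Five outcomes in two arms make 10 within-arm tests.

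- Independent outcomes: 1 − 0.975¹⁰ = 22.4%.
- Correlated outcomes, simulated with 25 per arm: about 18% at correlation 0.5 and 15% at 0.7.

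For the five between-arm tests, two-sided at 5%:

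- Independent: 1 − 0.95⁵ = 22.6%.
- Correlated, simulated: about 18% at 0.5 and 15% at 0.7.
- Counting only results that favour training: 1 − 0.975⁵ = 11.9% if independent, about 9% at 0.5.

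**4. A retest gain shared by both arms, with no training effect.** The Protocol gives neither a retest gain nor correlations between outcomes. Both are assumptions, shown over a range. The gain is in SDs of the change score and is the same for all five outcomes, with 25 per arm.

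| Assumed gain | H0 as worded rejected (correlation 0.7 to 0) | One between-arm QuickSIN test significant |
|---|---|---|
| 0.2 | 58% to 82% | about 5% |
| 0.3 | 80% to 97% | about 5% |
| 0.5 | 99% to 100% | about 5% |

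In the control arm alone, a gain of 0.2 makes at least one of the five outcomes significant in about 35% (correlation 0.7) to 58% (independent) of trials.

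The between-arm test stays at 5% because a gain common to both arms cancels in the comparison.

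**The case against.** **A hierarchy already exists.** Sections 2.1, 2.3 and 2.5.2 all point to speech in noise, and section 2.6.2 lists QuickSIN first. This stands. It would be wrong to say that the Protocol has no primary outcome. The fault is that sections 2.4 and 2.6.2 do not use the one it has.

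**H1 protects against a false claim.** A reader might infer that a practice gain among controls, or one chance result among five, would let the trial declare the training effective. The document does not support that. H1 requires gains greater than in controls, so a control-arm gain cannot meet it. If H1 needs every domain, the chance of meeting it falsely cannot exceed that of its least likely component, 2.5% for one test in favour of training. What remains is a null whose rejection says little about training.

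**The multiplicity rule may be in a statistical analysis plan that is not shown.** Agreed, and the absence of an adjustment is not counted as an error here. Such a rule would not repair hypotheses that are fixed in the Protocol and do not complement each other.

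**The word *and* in H0 could mean that all three domains must improve.** This is possible, and it would lower the rejection rates. An H0 open to both readings still needs rewording, and under either reading it lacks a between-arm comparison.

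**The error rates could be stated too high.** Taking 1 − 0.95¹⁰ = 40% for the ten within-arm tests would count significant worsening as well, which H0 does not mention; the improvement-only figure is 22%. Different QuickSIN lists at the two visits and the unscored practice run for the single and dual tasks (section 2.5.8) should reduce retest gains, though not necessarily to zero. Section 2.6.2 plans an ANCOVA, not separate paired tests in each arm, so the within-arm figures illustrate H0 as worded and not the planned model.

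**Conclusion.** The concern holds as a wrongly stated hypothesis pair that is out of line with the Protocol's own primary aim and sample size. Non-complementarity follows from the text alone and needs no assumption beyond the plain reading of H0. The size does rest on assumptions. With no true change, rejection of H0 as worded runs from 15% to 22% over correlations of 0.7 to 0. With a common retest gain of 0.2 SD of the change score it runs from 58% to 82%, and it is higher for larger gains. A single between-arm QuickSIN test stays near 5% throughout.

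The point does not show that the trial would falsely claim efficacy at those rates, and it does not call the design, the randomisation or the sample size into question. The wording should be corrected because the correction is cheap and settles in advance which comparison decides the trial.

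**What to change.** Reword section 2.4: *H0: mean final QuickSIN SNR loss, adjusted for baseline QuickSIN, does not differ between arms. H1: it differs.*

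Add to section 2.6.2 that this between-arm ANCOVA comparison, two-sided at 5%, is the single confirmatory test. State that HHIE, Glasgow disability, MCRM, the dual task and all within-arm (time) changes are secondary and supportive.

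The cost is a rewritten section 2.4 and a sentence or two in section 2.6.2. No participants, visits or measurements are added. The 25 per group still applies, since it was computed for this kind of comparison, and initial QuickSIN is already the planned covariate. The one loss is that a secondary outcome can no longer carry a claim on its own.

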2.5 Research Design

2.5.1 Participant Selection and Exclusion Criteria

This study will recruit existing hearing aid users attending for a reassessment appointment in the Wrexham Audiology service. They will have a need in their personal plan relating to improved speech perception in noise despite adequate aiding. Participants will have four-frequency average hearing thresholds greater than 20 dB HL. Participants will be recruited alongside a regular communication partner, either somebody who lives with them or who visits daily and is willing to complete the training programme with them. All participants (hearing aid users and communication partners) will also fulfill the following criteria: fluent and comfortable conversing in English, able to access the Wrexham Maelor Hospital Audiology Service, able to attend initial and followup appointments together, no significant self-reported memory problems or neurological problems. Participants should not have any reported colour-blindness. Participants will be aged between 65 and 85 years in order to reflect the main population of the BCU Audiology department. This is based on the mean age of patient attending for reassessment (75.37 years) \pm one standard deviation (13.19 years) rounded to 5 years. The inclusion of this criterion also helps to reduce the effect of ageing on results as it has been found that auditory training is more effective in younger people due to better neural plasticity (Baran, 2007). Any participants who do not meet these criteria will be excluded from the study.

2.5.2 Sample Size

Based on the research design below an a priori sample size calculation has been carried out using the reported effect size of 0.8 on the QuickSIN from Olson et al. (2013). An effect size of 0.8 indicated that 25 participants are needed in each group to give a power of 80% at 5% significance.

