2.2.2.1 Auditory Training Programmes Currently Available

Based on these principles a number of structured auditory training programmes are commercially available. A summary of commonly used programmes is given in Table 1. The LACE training programme is currently given to some Hearing Therapy patients in Betsi Cadwaladr University Health Board in order to improve their listening skills. Although these programmes are often used in the UK, Phonomena is the only

programme which was designed and developed here. This means that with other programmes, the speech stimuli used often have American accents which can increase the listening demand for users (Mattys et al., 2012). As can be seen in Table 1, training programmes require a large amount of commitment from the user to practice the tasks a few times per week for long periods of time. A systematic analysis by Henshaw and Ferguson (2013a) showed that compliance with programmes during research studies was relatively high (between 70 and 80%) however these results were not consistent with a clinical study involving users of the LACE programme in America where programme compliance was only 30% (Sweetow and Sabes, 2010). This suggests that the compliance rates shown in small scale research projects may not be representative of the clinical picture at large. While a computerised programme is beneficial as it can be carried out at home while providing real-time training information to the monitoring clinician via the internet, this delivery method may not be appropriate for all hearingimpaired listeners. In a survey of adults aged 50-74 years, Henshaw et al. (2012) showed that computer use varied with age. Computer and internet use was 81.0% and 60.9% respectively for the younger adults (aged 50-62 years) but reduced to 65.4% and 29.8% respectively for the older adults (aged 63-74 years). The mean age of patients attending for hearing reassessment in Betsi Cadwaladr University Health Board is 73.37 years. While these statistics do not discount computerised service delivery as an option, particularly in future as computer literacy increases, alternative delivery methods need to be available for many hearing-impaired listeners.

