2.2.2.2 Effects of Auditory Training

Studies evaluating the effect of LACE have shown positive results on a range of measures in the US (Sweetow and Sabes, 2006; Song et al., 2012; Olson et al., 2013) however the effectiveness of the programme for our patient group has yet to be evaluated. Following a four-week training programme using LACE statistically significant, and more importantly clinically significant, improvements in speech intelligibility in noise performance were reported by Sweetow and Sabes (2006) on the QuickSIN test (see Section 2.2.3 for a description of QuickSIN). These improvements were maintained 8 weeks post-intervention. Improvements were also seen on the Hearing in Noise Test (HINT) but these did not reach significance. Olson (2013) demonstrated improvement on the QuickSIN following LACE training with a large effect size (0.8) for experienced

Table 1. Summar	y of commonl	y used auditory	/ training programmes
-----------------	--------------	-----------------	-----------------------

Name	Aim	Format	Population	Stimuli	Adaptive	Time	Reference
Earobics	Improve spelling, reading and	Computerised	Children and adults	Recorded speech	Adaptive	15-20 minutes, 3 times per week	www.earobics.com
	language						
FastForWord	Improve speed of auditory language processing and reading abilities	Computerised	Children and adults	Speech and non- speech stimuli		30 minutes, 5 days per week, 3-4 months	www.innovative- therapies.com
Phonomena	Improve auditory discrimination, phonemic awareness and build language skills	Computerised	Children		Adaptive		www.mindweavers.com
Listening and Communication Enhancement (LACE)	Improving listening skills	Computerised	Adults	Stimuli: Speech - sentences Processes: speech in noise, cognitive tasks, compressed speech	Adaptive	20 minutes, 5 times per week, 4 weeks	Sweetow and Sabes (2006) www.laceuk.co.uk
Dichotic Inter- aural Intensity Difference	Improving binaural separation and integration	Non- computerised, normally in clinic	Children and Adults	Stimuli: speech - digits, CV pairs and sentences Task: dichotic listening	Difficulty level set by clinician	15-30 minutes, 3-4 times per week, 2-3 months	Weihing and Musiek (2007)

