2.2.3 Speech Intelligibility in Noise Objective Measure

The QuickSIN (Killion et al., 2004) was developed as a shortened and improved version of the Speech in Noise Test (Etymotic Research, Inc, 1993 cited in Killion et al., 2004). The QuickSIN includes 12 lists of six IEEE sentences which the participant has to repeat back. The sentences each contain five key words and are presented in four-talker babble. The QuickSIN is an adaptive test using a descending paradigm to establish the participant's signal-to-noise (SNR) loss. SNR loss is the dB increase in the signal-to-noise ratio required by the participant in order to identify 50% of the stimuli correctly relative to a person with normal hearing (Etymotic Research, Inc., 2006).

The QuickSIN may be used clinically to assess the benefit of amplification, or of different hearing aid features, on the patient's ability to understand speech in noise (Taylor, 2003). The QuickSIN has also been shown to be a sensitive tool for investigating the effects of auditory training on speech intelligibility in noise performance (Sweetow and Sabes, 2006; Olson et al., 2013). As discussed in Section 2.2.3 in a recent study by Olson et al. (2013) a large effect size (0.8) was shown on the QuickSIN for experienced hearing aid users following a period of LACE training. This recommends the use of this measure in the current study. The QuickSIN will be administered pre-and post-intervention to

investigate the effect of the training on participants' speech intelligibility in noise performance.

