2.5.6 Training Programme

The training programme used in this study will focus primarily on improving speech perception in noise. Participants will have a conversation with their communication partner in the presence of a single competing speaker presented in soundfield for 30 minutes, five times per week for four weeks. The training schedule used in this study is based on the well documented regimen used in the LACE training programme. The single-talker distractor will be formed of a selection of 30 minute extracts from four English language commercially available audiobooks. A range of male and female distractors will be used. A single-talker distractor has been chosen as studies have shown that the informational masking from an intelligible single-talker has a greater effect on performance than the energetic masking from speech-shaped noise (Brungart, 2001). These extracts will be recorded onto a CD which will be provided to the participants in order for them to complete the training programme at home. At the end of each 30 minute extract a tone will sound to alert the participant that the training session for that day is complete. Participants will be instructed to play the CD at a level which is challenging but comfortable (i.e. not too loud).

As previously stated, compliance for clinically administered auditory training programmes has previously been low. In order to improve compliance a spoken letter will be given to the participants after the tone at the end of their training session. An incentive will be given to participants completing the training programme by being entered into a prize draw to win £25 book tokens for gathering all of the letters.

The placebo training programme undertaken by the control group will involve the same period of training but in quiet. They will be given a blank CD which is segmented into 30 minute sections with the tone and compliance letter given at the end of the training session.

All training, placebo and intervention, should be carried out while the participant is wearing their hearing aid/s. If the participant has multiple programs for different listening environments they should complete the training while listening in the program most suited to the training situation i.e. everyday listening for the control group and background noise for the experimental group.

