4.3 Impact of Research on Normal Workload

This study forms part of a clinical training programme for the Principal Investigator whose time is externally funded. Therefore, the time spent by the Principal Investigator on this project is not included in the summary of costs.

Data collection is expected to take 100 hours of clinical time. Research Audiologists will be involved in data collection, undertaking three-quarters of the total research appointments (the remaining quarter will be covered by the Principal Investigator). Part of the funding for this research will be used to backfill lost clinical sessions. The cost of the

02/09/13 30/09/13 28/10/13 25/11/13 23/12/13 20/01/14 17/02/14 17/03/14 14/04/14 12/05/14 09/06/14 07/07/14 04/08/14 01/09/14 29/09/14

Figure 4 Gantt chart showing timescale of project

Table 3 Costs involved in the research project

	Cost (£)	Justification
Staff costs	1753.73	 Backfill of clinical time lost through project: Mid-point Band 6 Audiologist, 75 hours x £18.77 including on-costs Mid-point Band 8 Audiologist, 10.5 hours x £32.95 including on-costs As completion forms part of a clinical training programme for the Principal Investigator all time spent on aspects of the project are covered under the terms of the training programme and are therefore not included in the staff costs. NHBRU staff researchers' time is funded by the NIHR.
Materials and consumables	115	Stationary (paper, envelopes etc.): £12.50 Postage: £37.50 Recordable CDs: £40 Voucher for prize draw: £25
Travel	1420	Travel costs for additional journeys undertaken by research participants: 25 participants with 1 additional journey, £10 per journey 25 participants with 2 additional journeys, £10 per journey Travel for meetings between researchers £670
Apparatus and	125	Purchase of QuickSIN
Total	3413.73	

additional workload generated by this study have been included in the above research costs (see Table 3).

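### The 80% power is not justified: 0.8 is described only as improvement after a different programme, yet it is used as the difference from a placebo training arm, with no allowance for loss

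*Protocol*

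**What the plan says.** Protocol section 2.5.2 takes an effect size of 0.8 on the QuickSIN from one cited study and concludes: "An effect size of 0.8 indicated that 25 participants are needed in each group to give a power of 80% at 5% significance". It names no test and no sidedness, and gives no SD, baseline correlation or dropout rate.

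The 0.8 is described twice elsewhere. Section 2.2.2.2 says the cited study "demonstrated improvement on the QuickSIN following LACE training with a large effect size (0.8) for experienced" hearing aid users. Section 2.2.3 says "a large effect size (0.8) was shown on the QuickSIN for experienced hearing aid users following a period of LACE training". Neither sentence mentions a comparison group.

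The contrast in this trial is set by three other sections. H₁ in section 2.4 requires the trained group to improve significantly more than the control group. On that control group, section 2.5.6 says: "The placebo training programme undertaken by the control group will involve the same period of training but in quiet". Under section 2.5.5 all outcome measures are taken at both appointments, and section 2.5.8 applies the components to all participants, so controls are retested as well.

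Section 2.6.2 plans an ANCOVA with initial QuickSIN as covariate. Section 3.3 lets participants withdraw at any time. Table 3 costs travel for 25 participants with one extra journey and "25 participants with 2 additional journeys, £10 per journey". Section 4.3 expects 100 hours of data collection.

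**The concern.** A power calculation is only as good as the match between its effect size and the contrast being tested. The 0.8 is reported as what happened after LACE. The trial tests how much more people gain from a different programme than from a placebo programme of equal duration. Any gain in controls from practice, attention or retesting shrinks the between-arm difference, and section 2.2.6 itself says that it is unknown whether the new format works. Section 2.5.2 carries 0.8 across unchanged and does not say why.

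Planned enrolment also equals the number the calculation asks for, so nothing is held back for withdrawals.

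What is at stake is the reading of a null result. A reader who trusts the 80% would take a non-significant QuickSIN comparison as fair evidence against the programme, when the trial may have had about an even chance, or less, of detecting a moderate effect.

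**Working it through.** **Inputs from the protocol.** Effect 0.8, significance 5%, power 80%, 25 per group (2.5.2); allocation 1:1 (2.5.3); ANCOVA on initial QuickSIN (2.6.2); two 60-minute appointments (2.5.5); 100 hours (4.3); Table 3 travel costs.

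**Assumed, because the protocol gives no value.** Net between-arm effect 0.6 or 0.5 SD, which is what remains of 0.8 if it is a gain on the raw SD and controls gain 0.2 or 0.3 SD; baseline-to-final correlation r of 0.5 or 0.7; 20 completers per arm as an example of 20% loss.

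**1. The plan's own figure.** Two independent groups, two-sided 5%, normal approximation:

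n per group = 2(1.960 + 0.842)² / 0.8² = 24.5, rounded up to 25.

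With the exact noncentral t, 25 per group gives 79.1% power, and 26 are needed to pass 80%. The stated figure therefore reproduces. Alternatives do not give 25: a one-sided two-group test needs 20 (21 by exact t), and a paired test in a single group needs 15. So 0.8 entered the calculation as a between-arm difference.

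**2. Planned enrolment.** Travel: 25 × 1 × £10 + 25 × 2 × £10 + £670 for researchers' meetings = £1,420, the Table 3 figure. Clinic time: 50 participants × 2 appointments × 1 hour = 100 hours. Both correspond to exactly 50 participants, so no loss is provided for.

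**3. Power over a range of net effects.** Two-sided 5%, noncentral t, with noncentrality d√(n/2) for n per arm. For ANCOVA, d is replaced by d/√(1 − r²). For example, 0.6/√0.75 = 0.69 and 0.5/√0.75 = 0.58.

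| Net effect (SD) | Per arm | Unadjusted | ANCOVA, r = 0.5 | ANCOVA, r = 0.7 |
|---|---|---|---|---|
| 0.8 | 25 | 79% | 89% | 97% |
| 0.6 | 25 | 55% | 67% | 83% |
| 0.5 | 25 | 41% | 52% | 68% |
| 0.8 | 20 | 69% | 81% | 93% |
| 0.6 | 20 | 46% | 57% | 73% |
| 0.5 | 20 | 34% | 43% | 58% |

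The first row applies only if 0.8 is a true between-arm effect scaled on the raw outcome SD.

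**4. Scaling.** The protocol does not say which SD the 0.8 was divided by. If it was the SD of change and r = 0.7, then 0.8 × √(2(1 − 0.7)) = 0.62 raw SD. Taking off an assumed control gain of 0.2 leaves 0.42, and ANCOVA power with 25 per arm is 53%.

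**5. What the design can detect.** An unadjusted comparison has 80% power for 0.81 SD with 25 per arm and for 0.91 SD with 20 per arm.

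**The case against.** The strongest reply is that the arithmetic is sound and the planned analysis is more powerful than the calculation assumes. If 0.8 is a genuine between-arm effect on the raw SD, ANCOVA with r = 0.5 gives 89%, and still 81% with 20 completers per arm. Even a net 0.6 reaches 83% with r = 0.7. Different QuickSIN lists at the two appointments (2.5.8) limit list-specific learning, so the retest gain in controls may be small. The protocol also has a progress call, an incentive and a sample it expects to be motivated (2.5.5, 2.5.6, 3.2).

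Much of this stands, and it rules out three stronger readings:

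- *That 0.8 is a single-group before-after effect.* This is a natural reading of sections 2.2.2.2 and 2.2.3, but neither says so and the cited study is not at hand.
- *That power is certainly below 80%, or reaches 80% only if everyone completes.* The first and fourth rows of the table show otherwise under favourable assumptions.
- *That 20% to 30% loss, or worse, should be expected.* The 70–80% and 30% in section 2.2.2.1 are rates of compliance with training programmes. A participant who skips sessions can still attend the final appointment and supply a QuickSIN score. No section gives a dropout rate.

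The reply does not supply the missing justification. The protocol states no baseline correlation and does not rely on one. It does not say what kind of effect 0.8 is, or why it should carry over to another programme and a placebo comparator. Reproducible arithmetic does not answer a doubt about the input.

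**Conclusion.** The point holds in this form: 0.8, described only as improvement following LACE, is used unchanged as the difference from a placebo arm with the same training period and the same retests, and no loss is allowed for. The 80% is therefore not justified and may be substantially lower.

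The true power cannot be determined from the document. With 25 per arm, a net effect of 0.6 to 0.5 SD gives 55–41% unadjusted, 67–52% by ANCOVA at r = 0.5 and 83–68% at r = 0.7. If 0.8 is a true between-arm effect on the raw SD, ANCOVA at r = 0.5 gives 89%, or 81% with 20 per arm. The net effects, correlations and completer numbers are all assumptions.

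Severity is should-fix. The number of participants need not change, but the stated power will be used to interpret a null result.

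**What to change.** Keep 50 participants and rewrite section 2.5.2 so that it:

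- says what kind of effect the 0.8 is (before-after or between groups, and on which SD), or states that this is not known;
- gives, for the planned ANCOVA on final QuickSIN, the sidedness, the assumed between-arm difference net of any control gain, the SD, the baseline correlation and the expected number of completers;
- replaces the unqualified 80% with a range of power over those assumptions;
- adds that an unadjusted comparison of 25 per arm detects 0.81 SD at 80% power, or 0.91 SD with 20 completers per arm.

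The compliance rates in section 2.2.2.1 should not be used as the dropout assumption. The sponsor will have to supply the SD, correlation and completion rate, since the protocol does not contain them.

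The cost is one rewritten paragraph and a stated power that is likely to look less favourable. Recruitment, budget and procedures stay as they are.
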